3.3. End of Treatment (EOT) Evaluation/Early Withdrawal

EOT visit should be conducted 14 or 21 days (± 2 days) after last infusion, depending on last infusion was given on Day 8 or Day 1, respectively. Early withdrawal visit should be conducted after the subject receives the last dose of study treatment.

The following assessments will be performed at the EOT/early withdrawal visit:

- Physical examination
- Vital signs
- ECOG performance status
- AEs
- Concomitant medication
- 12-lead ECG
- Tumor assessment (radiological imaging)
- Laboratory tests (hematology, clinical chemistry and coagulation)
- Urinalysis

3.4. Follow-up

After discontinuation of study treatment, all subjects will be followed for survival and disease-specific therapies of the clinician's choice will be administered. The data will be collected and can be done by telephone. Follow-up visits will be scheduled every 3 weeks for 9 weeks, thereafter every 9 weeks until the end of the study.

3.5. Unscheduled Visit

The following assessments will be performed during an unscheduled visit:

- Physical examination
- Vital signs
- ECOG performance status
- AEs
- Concomitant medication
- 12-lead ECG*

- Tumor assessment (radiological imaging)*
- Laboratory tests* (hematology, clinical chemistry and coagulation)
- Urinalysis*

*To be performed when necessary at the subject's request or per Investigator decision.

3.6. Study Design, Including the Choice of Control Groups

There is no control group in this Phase II study. The rationale for the study is discussed in [Section 1.2](#).

3.7. Selection of Study Population

3.7.1. Inclusion Criteria

1. Aged ≥ 20 years;
2. Signed informed consent obtained prior to initiation of any study-specific procedures and treatment;
3. Histological or cytological confirmed squamous cell carcinoma of head and neck, excluding nasopharyngeal carcinoma;
4. Subjects with unresectable, unfeasible radiotherapy, recurrent or metastatic head and neck squamous cell carcinoma, after previous treatment with platinum agent;
5. Subjects must have at least one measurable tumor lesion as defined by RECIST version 1.1 as assessed by the investigator (local radiological image assessment) or clinically evaluable disease. Physical and neurological examinations, and radiographic studies have to be performed within 28 days of Cycle 1 Day 1;
6. Eastern Cooperative Oncology Group (ECOG) Performance Status (PS) 0-1;
7. Life expectancy of 12 weeks or longer;
8. Concurrent local therapy is not allowed, but concurrent palliative radiation therapy to non-measurable sites of disease such as painful bone metastasis is permitted;
9. All eligible subjects of childbearing potential have to use effective contraception; that is, double barrier contraceptive methods;
10. Documented progressive disease within past 6 months;
11. Adequate bone marrow reserve, cardiac, renal and liver function:
 - a. Absolute neutrophil count (ANC) $> 1.5 \times 10^9/L$;
 - b. White blood cell (WBC) $> 3 \times 10^9/L$
 - c. Platelet count $> 75 \times 10^9/L$;
 - d. Hemoglobin $> 9 \text{ g/dL}$ ($> 5.6 \text{ mmol/l}$);

- e. Prothrombin time (PT)/international normalized ratio (INR) ≤ 1.5 x upper limit of normal (ULN)
- f. Creatinine clearance (Cockcroft & Gault formula) >50 mL/min;
- g. Alanine aminotransferase (ALT, SGPT) and aspartate aminotransferase (AST, SGOT) and Alkaline Phosphatase (ALP) < 3 x ULN; AST/ALT ≤ 5 x ULN if liver metastasis
- h. Serum albumin ≥ 3 g/dL;
- i. Total Bilirubin ≤ 1.5 x ULN
- j. QTc < 450 msec

3.7.2. Exclusion Criteria:

1. Known primary CNS malignancy or CNS involvement (except for brain metastases that have been treated and are stable and subject is off steroids);
2. Chemotherapy, radiation therapy, major surgery or investigational agents including immune or target therapies less than 4 weeks prior to study drug treatment;
3. History of malignancy other than head and neck cancer with the exception of early stage non-melanoma skin cancer or carcinoma *in situ* of cervix;
4. History of liver cirrhosis;
5. Active hepatitis B or hepatitis C infection
6. Clinical significant pulmonary obstructive or clinical significant pulmonary restrictive diseases (grade >2);
7. Clinically significant cardiac disease (NYHA class > 2);
8. Other serious illness or medical conditions, such as active infection, unresolved bowel obstruction, or psychiatric disorders;
9. Known HIV positivity;
10. Pregnant or breast-feeding subjects, and men and women of child-bearing potential not using effective contraception while on study treatment;
 - For females of child bearing potential (without using hormonal contraceptives for at least 2 months prior to start of screening) a double contraception method is required during the entire study meeting the criteria for an effective method of birth control, i.e. at least two effective birth control methods* (1 of which must be a barrier method) such as condoms, diaphragms or intra-uterine devices must be used.
 - * Acceptable forms include:
 - Consistent and correct usage of established oral contraception.
 - Established intrauterine device or intrauterine system.
 - Barrier methods of contraception: condom or occlusive cap (diaphragm or cervical/vault caps) with spermicidal foam/gel/film/cream/suppository
 - Male participants with partners of child bearing potential are required to use barrier contraception in addition to having their partner use another method of contraception during the trial and for 3 months after the last dose. Male participants will also be advised to abstain from sexual intercourse with pregnant or lactating women, or to use condoms.

11. Known hypersensitivity to any component of SCB01A or excipients including Solutol[®], alcohol, and PEG300;
12. History of exposure to SCB01A or its analogues;
13. History of active or significant neurological disorder or psychiatric disorder that would prohibit the understanding and giving of informed consent, or would interfere with the clinical and radiological evaluation of central nervous system during the trial;
14. Peripheral neuropathy (\geq grade 2);
15. Any other reason the investigator deems the subject to be unsuitable for the study.

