4.12. Prohibited Medications

Subjects are prohibited from using any of the following medications during study:

1. Any investigational drug, chemotherapy, targeting agent(s), biology therapy, immunotherapy, herbal medicine or hormonal therapy administered within 4 weeks before the date of the first study treatment should be excluded from enrolment until at least 4 weeks have passed.
2. Concomitant administrations of compounds that inhibit CYP1A2 or CYP2D6 are prohibited for 3 weeks prior to study drug infusions and throughout the study. Excluded concomitant medications of CYP1A2 and CYP2D6 inhibitors include (except antibiotics whenever they are clinically indicated): fluvoxamine, ciprofloxacin, cimetidine, bupropion, cinacalcet, fluoxetine, paroxetine, quinidine, duloxetine, sertraline, terbinafine and amiodarone.

Note: 1. 5-HT₃ antagonist (serotonin antagonist) with the antiemetic effect can be used as a substitute for metoclopramide in preventing nausea and vomiting activity. 2. Steroid can be used as a substitute for diphenhydramine in treating allergies.

3. Therapy with anticoagulants, antiplatelet treatments (e.g. Warfarin, heparins) are not allowed during the study.

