5.1. Medical History

Medical history will be assessed at screening and will include the following:

1. Histological or cytological confirmed metastatic squamous cell carcinoma in head and neck.
2. At least one measurable tumor lesion according to RECIST version 1.1 as assessed by the investigator (local radiological image assessment).
3. Details of the prior therapy that failed or intolerable to platinum agent and also not amenable to further surgical or radiation therapy due to disease progression or toxicity.
4. Smoking status (current smoker or past history of smoking).
5. Betel nut consumption status or history.
6. Additionally, all relevant medical histories, medical conditions, or symptoms experienced during 30 days prior to screening are to be recorded, using the body system categories outlined below. For each history, the specific medical terminology for the disease/disorder/condition, the date of diagnosis, and the history status (resolved or ongoing) will be documented. Surgery and procedure: within 1 year prior to screening visit should be recorded, cancer history should be recorded on life time base.

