6.1. Efficacy Measurements

Tumor response will be assessed by using computerized tomography (CT) or MRI scans according to RECIST v1.1 at baseline and at the end of Cycle 3 (at C3D21/EOT visit). For subjects who are continuing treatment beyond 3 cycles (9 weeks), tumor assessment will be performed at every three cycles until progression of disease (i.e. at or prior to Day 1 of Cycles 4, 7, 10 and so on). Any additional assessments can be arranged when clinically indicated.

Scans must include brain, chest, abdomen, and pelvis. The imaging technique used at baseline should be used throughout the study.

Subjects will be considered evaluable for tumor assessment in this study if they fulfill the criteria for evaluation according to RECIST v1.1, i.e., those subjects who undergo a baseline disease assessment within 4 weeks of treatment initiation, and who undergo at least 1 disease assessment on study (the following should be revised if revision in corresponding part in synopsis is accepted).

- ORR is defined as the percentage of subjects who have achieved confirmed CR and PR at a particular time point after first treatment, according to RECIST v1.1.
- PFS is defined as the time from the start of treatment up to the date of first progression based on RECIST v1.1 or the date of death, whichever comes first.
- OS is defined as the as the time from the start of treatment up to the time that the subject is still alive.
- Best overall tumor response defined as an objective response or stable disease of treatment phase.

Survival data will be collected throughout the active treatment phase and during the follow-up period. Survival follow-up after subject discontinuation of treatment will be conducted every 3 weeks during the first 9 weeks, thereafter every 9 weeks until the end of the study.

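### Criterion 10 does not tie progression to the last anticancer therapy, and the baseline scan may coincide with its end, so late shrinkage from that therapy could be scored as a response to SCB01A

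*Protocol*

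**What the plan says.** **Eligibility.** Protocol section 3.7.1 (and the synopsis) sets two conditions on disease history. Criterion 4 asks for recurrent or metastatic disease "after previous treatment with platinum agent". Criterion 10 asks for "Documented progressive disease within past 6 months". Neither says which therapy the progression must follow.

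**Washout.** Exclusion criterion 2 in section 3.7.2 rules out "Chemotherapy, radiation therapy, major surgery or investigational agents including immune or target therapies less than 4 weeks prior to study drug treatment". Section 4.12 repeats the interval for systemic agents "administered within 4 weeks before the date of the first study treatment should be excluded". Treatment that ended exactly four weeks before the first dose is therefore allowed.

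**Baseline scan.** Criterion 5 says that "radiographic studies have to be performed within 28 days of Cycle 1 Day 1", and section 6.1 counts as evaluable those "who undergo a baseline disease assessment within 4 weeks of treatment initiation". Table 1 gives the screening window as Day -28 to Day -1. No section says that the scan must follow the end of prior therapy.

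**Endpoint.** The primary endpoint is confirmed CR plus PR by RECIST 1.1 (synopsis; section 6.1; SAP section 9.8). The confirmatory scan is at least 4 weeks after the first. No definition has a rule for effects of earlier treatment. Section 3.6 states that there is no control group.

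**Prior therapy.** The title and the aim in section 1.2 describe subjects who have failed platinum. Section 5.1 lists, as a medical-history item, "Details of the prior therapy that failed or intolerable to platinum agent".

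**The concern.** Take a subject who progressed five months ago, then received another regimen, and whose tumour was stable or shrinking when that regimen stopped four weeks before Cycle 1 Day 1. The scan taken that day is an acceptable baseline. On these points the subject meets criteria 4, 5 and 10 and is not caught by exclusion criterion 2. If the tumour goes on shrinking because of the earlier regimen, the shrinkage is measured against that baseline and credited to SCB01A.

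The question is one of attribution. It is separate from whether subjects failed platinum, because a subject can have failed platinum and still carry benefit from a later regimen.

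It matters here because the null rate is low and the decision turns on very few responses: one in 10 opens Stage II, and four in 29 meet the primary objective.

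**Working it through.** **1. The plan's design (protocol section 8.2).** Inputs: P0 = 0.05, P1 = 0.20, 10 then 19 evaluable subjects, stop at 0/10, success at 4/29 or more. With X the number of Stage I responders,

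P(success) = sum over x ≥ 1 of P(X = x) × P(Bin(19, p) ≥ 4 − x).

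At p = 0.05:
- x = 1: 0.3151 × 0.0665 = 0.0210
- x = 2: 0.0746 × 0.2453 = 0.0183
- x = 3: 0.0105 × 0.6226 = 0.0065
- x ≥ 4: 0.0010

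The sum is 0.0468. At p = 0.20 the same formula gives power 0.801. The probability of stopping early under P0 is 0.95^10 = 0.599. A search over two-stage designs returns this one as optimal, and 29/(1 − 0.20) = 36.25, rounded up to 37. The plan's arithmetic is right.

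**2. The guaranteed gap.** Minimum washout of 28 days minus maximum scan lead of 28 days = 0 days between the end of prior therapy and the baseline scan.

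**3. One carried-over responder, SCB01A's own ORR 5%.** This needs no carry-over rate.
- In Stage I the subject alone passes the futility gate. Success then needs 3 or more among the other 28: P(Bin(28, 0.05) ≥ 3) = 0.163.
- In Stage II the gate must be passed by others, and 3 more responders are needed among 10 + 18: 0.3151 × 0.2265 + 0.0746 × 0.6028 + 0.0115 = 0.128.

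**4. Assumed mixtures.** Let c be the share of subjects exposed to carry-over and s the chance of a late confirmed response in each. Both are assumptions.
- If SCB01A's own ORR is 5%, the observed rate is p = 0.05 + 0.95 × c × s.
- If SCB01A produces no responses, p = c × s.

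Each p goes into the formula in step 1.

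| c | s | p, own ORR 5% | P(success) | p, own ORR 0 | P(success) |
|---|---|---|---|---|---|
| 5% | 10% | 5.5% | 0.061 | 0.5% | < 0.001 |
| 10% | 15% | 6.4% | 0.097 | 1.5% | 0.0007 |
| 10% | 25% | 7.4% | 0.140 | 2.5% | 0.005 |
| 20% | 15% | 7.9% | 0.165 | 3.0% | 0.009 |
| 20% | 25% | 9.8% | 0.274 | 5.0% | 0.047 |

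**5. Expected number of late responses in 29 subjects, 29 × c × s.** For c = 10% and s = 15-25% it is 0.4-0.7. For c = 20% and the same s it is 0.9-1.5.

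**The case against.** **The route is narrow.** It needs progression, then another regimen, then a stop without progression close to Day -28, and an early scan. The zero-day gap is the boundary case. The title and aim suggest that most subjects will have progressed on their last regimen, and exclusion criterion 15 lets the investigator decline a subject. This stands as a limit on frequency, but no operative criterion closes the route.

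**Confirmation filters some of it.** The first on-study scan falls at about Day 64 and confirmation at least 4 weeks later. If therapy ended on Day -28, the carried-over response must be present about 13 weeks after the last prior dose and last to about 17 weeks. That removes short-lived shrinkage. It does not remove durable shrinkage, because both scans are compared with the same baseline.

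**The direction is not fixed.** Where a tumour grows during the time off therapy, an early baseline scan understates the burden at first dose and works against scoring a PR. The net effect of the scan window on ORR is therefore unsigned. The attribution gap remains for those whose tumours are still shrinking.

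**Stronger readings that the documents do not support.**
- A reader might infer that an inactive drug would pass with probability 0.10-0.27. Those values belong to a drug already at 5% with carry-over added. With no responses of its own, the same assumptions give 0.047 or less. The documents give no source for P0, so it cannot be settled whether 5% already includes such effects.
- A reader might expect several carried-over responders. Step 5 gives 0.4-1.5.
- A reader might take section 5.1 as showing that the last therapy may have been stopped while it was working. It is a recording item about intolerance to platinum, not an eligibility rule about the most recent therapy, and such a subject still needs documented progression under criterion 10.

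**Conclusion.** The gap in the text is real. Criterion 10 is tied to no therapy, the guaranteed interval between prior therapy and baseline scan is zero, and neither the endpoint definition nor a control arm separates late effects of earlier treatment. The size of the bias cannot be derived from the documents. What can be said is conditional: at an own ORR of 5%, a single misattributed responder takes the false-positive probability to about 2.7 times (Stage II, 0.128/0.047) or 3.5 times (Stage I, 0.163/0.047) its planned value. The 0.061-0.274 range rests wholly on the assumed shares. The sample-size calculation is not in question. This is an inexpensive improvement to attribution, not evidence that the trial's result would be wrong.

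**What to change.** 1. **Section 3.7.1, criterion 10, and the synopsis:** require progressive disease documented on or after the most recent anticancer treatment. This also makes the criteria agree with the failed-therapy wording of the title and aim.
2. **Sections 3.2.1 and 6.1:** state that the baseline scan is taken after the last dose of prior therapy, within the existing 28-day window. The documents give no basis for a fixed minimum interval, so none is proposed.
3. **SAP:** list for each responder the last prior therapy, its end date, the date of last progression and the baseline scan date. Add a sensitivity ORR that counts responders without progression after their last therapy as non-responders, and re-read the 4-of-29 rule on that count.

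**Cost.** No added subjects; the numbers stay at 29 evaluable and 37 recruited. A few candidates may be excluded, or scanned later or a second time in screening. Part 3 uses data that are largely collected already: section 3.2.1 records all prior anti-tumour therapy and the baseline imaging, and criterion 10 already requires the progression to be documented. The SAP text is in the past tense, so enrolment may be over. Part 3 can still be done then, and would show whether any responder is affected.

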3.8. Removal of Subjects from Treatment or Assessment

3.8.1. Early Discontinuation of the Study

The study may be discontinued at the sole discretion of the Sponsor for any reason, including medical or ethical reasons affecting the continued performance of the study, or difficulties in the recruitment of subjects.

The study may also be discontinued based on evidence of either substantial efficacy, or likely failure to meet the primary objective.

3.8.2. Early Discontinuation of Individual Subjects

The investigator may remove a subject from study treatment at his/her discretion for any of the following reasons:

- Disease progression
- Intolerable AE(s) or failure to tolerate the study treatment
- Subject decides to discontinue study therapy
- Any medically appropriate reason or significant protocol violation, in the opinion of the investigator
- Lost follow-up

Subjects may decide to discontinue study treatment for any reason. Subjects who elect to discontinue study treatment should be encouraged to continue in the study so that follow-up information on disease progression and survival status may be obtained. However, subjects may elect to withdraw consent and decline further participation in the trial.

All subjects will be followed until disease progression, withdrawal of consent, intolerable AEs/toxicity, death, loss to follow-up or the end of the study.

The investigator must determine the primary reason for a subject's discontinuation of study treatment and record this information on the CRF. Subjects who are prematurely withdrawn from study treatment are not eligible to re-initiate study treatment on this protocol at a later date.

4. Treatments

4.1. Identity of Investigational Product (IP)

SCB01A (a novel heterocyclic CA-4 analogue) is dissolved in absolute EtOH, PEG 300, and Solutol[®]. Solutol[®] (Macrogol 15 Hydroxystearate) is a non-ionic solubilizer for injection solutions and conforms to the requirements of the European Pharmacopoeia monograph. PEG 300 (Macrogol 300) is a mixture of polymers of ethylene oxide and water and their ethers. The average molecular weight is about 300 and conforms to the requirements of the European Pharmacopoeia monograph. Dehydrated alcohol contains > 99.2% by weight, corresponding to > 99.5% by volume at 15.56°C of C₂H₅OH and conforms to the requirements of the US Pharmacopoeia monograph.

SCB01A is a water insoluble, white to slightly yellow solid. At room temperature, the water solubility of SCB01A is 0.9 µg/ml. Formulated SCB01A is a sterile, clean, colorless to slightly yellow viscous solution.

4.2. Study Drug Packaging and Labeling

The study drug is packaged in glass vials with a rubber stopper and flip-off seal labeled with the study protocol number, contents, directions for use, storage directions, clinical trial statement, and sponsor name.

4.3. Study Drug Storage Conditions

Formulated SCB01A can be stored at temperatures 15-25 °C. Although direct data on its photosensitivity is unavailable, the avoidance of light is recommended.

4.4. Study Drug Dose Preparation and Administration

The study drug, SCB01A is packaged as 10 mg/ml in 5 ml/vial. The injection volume of SCB01A should be calculated based on the BSA of the subject. (See [Section 5.3](#)). The study drug will be diluted in normal saline solution before infusion. An equal volume of normal saline will be drawn out from a 250 ml normal saline container before adding the SCB01A injection solution. The total volume of study drug diluted solution will be equal to 250 ml. The study drug should be administered for 24 hours (time window 24 hours±10 mins) by i.v. infusion through a central line in order to avoid potential extravasation and tissue necrosis. The duration from drug dilution to completion of 24h i.v. infusion must not exceed a maximum of 28 hours. For further details, please refer to the IMP Manual.

4.5. Study Drug Accountability

Drug Accountability records will be maintained by the study sites. All used and partially used supplies of SCB01A will be destroyed by the study site in accordance with institutional policies after accountability performed by the monitor. The site will maintain detailed documentation of the number and identification of vials, which are

used and destroyed, and copies of these documents will be provided to the sponsor or Clinical Research Organization (CRO). Disposition of all unused study drug will be carried out according to instructions provided by the sponsor or CRO at the end of the study and after a final drug accountability assessment is performed by the monitor.

4.6. Method of Assigning Subjects to Treatment Groups

There is no randomization in this study. All subjects will receive the study drug, and the dose as per intra-subject dose escalation plan. Subjects will be assigned to Dose 1 (12 mg/m²) initially on Days 1 and 8 of Cycle 1. If the subject experiences no DLT during this period, dose escalation of SCB01A to Dose level 2 (18 mg/m²) occurred from Cycle 2; and increased to Dose level 3 (24 mg/m²) on Cycle 3.

